#### 7. Data Collection:

As with any study, we will take significant steps to safeguard all personal health information collected. We will only collect the minimal amount of personal health information required as described above. All files will be deindentified and disassociated from practice identifiers as soon as the study is complete. All records will be kept in locked offices, on password protected computers and in password protected files. Finally, all data submitted to the QuIIN QIDA national collaborative will be deidentified to the extent described above. QuIIN, using the QIDA software, has performed these activities on multiple prior QIC projects without any breaches of confidentiality. The QIDA system is web-based and HIPAA compliant, and QuIIN will take responsibility for data security. Only the research team will have access to the raw QIDA data, and all data will be kept on password protected computers in locked offices. No patient identifiable information is stored in the QIDA database. Project data will be stored for 7 years in the QIDA system, but once a project closes, only AAP QIDA staff will have access to the data. As such the risk of a breach of confidentiality is minimal and the legal risks associated with a breach of confidentiality are also be minimal.

There will be 6 sets of data submitted to the QuIIN Quality Improvement Data Aggregator (QIDA) program. First, all practices will report demographic data annually, including patient volume, number and training level of physician or physician assistant-level providers, number of nursing and office staff, university-affiliation, EHR availability, presence of trainees, and prior self-reported work aiming to improve these diagnostic errors. This demographic practice-level data will not include any PHI, aside from the contact information sought as with most project applications initially. The project application will serve as the first set of practice-based demographic data and it will be requested 2 additional times.

Second, each practice will collect data on 1) incidence of adolescent depression (number of adolescents diagnosed with depression or subsyndromal depression as defined by

the problem list or patient notes per 100 adolescent visits), 2) missed diagnosis of pediatric elevated blood pressure (elevated systolic or diastolic blood pressure for age, gender and height without provider recognition per 100 elevated blood pressures measured) and 3) delayed diagnosis of actionable laboratory results (number of delayed actions, as defined in Table 2, per 100 abnormal laboratory evaluations received). All of this data will originate from paper or electronic patient charts. For each of the charts screened, the following demographic data will also be recorded: age, gender and insurance status. These data will be entered into QIDA without patient names or birthdates. No PHI will be recorded as part of this dataset that will be collected monthly.

The third set of data submitted will be process measure data for each of the three diagnostic errors described in the grant. These data will be submitted by practices assigned to the related diagnostic error while they are actively intervening on that error (i.e. for 8 months the group randomized to intervene on adolescent depression will collect process measure data on screening for adolescent depression). The three process measures will be 1) the percent of adolescents screened for depression, 2) the percent of children  $\geq$ 3 years old receiving blood pressure measurement at triage, and 3) the percent of providers with laboratory results unread or unacknowledged in their EHR inbox for more than 72 hours. These data will be entered in aggregate into QIDA for each clinic monthly and collected via electronic health record or practice based paper charting methods in each practice.

The fourth set of data collected will be mini-root cause analyses, which identify patient and systems level factors that could have contributed to 1 diagnostic error monthly. Each practice will examine standardized patient, provider and systems factors that could have led to the specific diagnostic errors identified in this grant. These factors could include 1) patient factors of age, gender, reason for visit, patient comorbidities, language barriers, acute illness, agitation of patient/family, social issues, etc. , 2) provider factors of type of provider, provider level of training, provider fatigue/impairment, personal stressors of providers, provider disagreements, provider knowledge, provider beliefs about the project or the patient, etc. and 3) systems factors of time of visit, clinic milieu during visit (chaotic vs. calm), increased workload, staffing concerns, verbal/written communication, computer software or hardware, non-computer equipment, etc.. These mini-root cause analyses factors will be collected on paper based forms, deidentified and entered into SurveyMonkey. Practices will be encouraged to identify and spread lessons learned to all providers in their practices to prevent future errors.

The fifth set of data collected will be related to providers' abilities to recognize abnormal findings that could relate to the diagnostic errors of interest. As recognition of abnormal findings is key to ultimately making a correct diagnosis, it is important for practices to track and understand if their clinicians are appropriately recognizing abnormal results. These data will be obtained by electronic and paper chart review of the same 10-17 charts per month as the primary outcome measures noted above. They will include: 1) Percent of charts with documentation of patient's systolic and diastolic blood pressure percentiles documented in the record, 2) Percent of charts with documentation of mental health concerns in patient record or 3) Percent of charts with abnormal actionable laboratory results noted as "abnormal" in the patient record. Clinics will only collect these data when they are the intervention or control group for a given measure.

The final set of data will be aggregate data of patients one time during the 2 year collaborative to identify the time between when the appropriate information to diagnose the patient was available and when the actual diagnosis was conveyed to the family. Practices who have intervened on a given error will track 50 patient charts with one of the following metrics: 1) time between positive mental health screen and diagnosis of depression or depression diagnosis ruled out, 2) the number of days between blood pressure elevation in the medical record and notification of the family, or 3) time between abnormal laboratory result received and notification of family, we will ask practices to identify, in the same 50 patients with

a delayed diagnosis of actionable laboratory results 6 months after the diagnostic opportunity to evaluate for emergency department visits, clinic visits, ultimate diagnosis, clinical worsening in laboratory values and other patient morbidities. Similarly, we will ask intervention practices to evaluate 50 patients whose diagnostic instrument of the PHQ-9M was positive 6 months after the diagnostic opportunity to evaluate how many were ultimately diagnosed with depression, attended initial mental health appointments and were referred to mental health or were diagnosed directly by the pediatrician.. This final set of data will be collected only once between 12-18 months after the intervention period begins.

For research and publications that may result from this work, all data will be reported in aggregate, and individual and practice data will not be identifiable. If practice data is presented, each practice will receive an ID number in the report. Potential publications may include a conceptual model of key barriers and potentially useful strategies that emerged from this project. No patients or practice staff will be identified in any report or publication about this study. Practice names will only be used in the acknowledgement section of any potential publication.

Statistical Models: The primary independent variable will be assignment to the control or QIC group and the 3 primary dependent variables will be the adolescent depression rate (number of adolescents diagnosed with depression per 100 adolescent visits), the missed pediatric elevated blood pressure rate (elevated blood pressure not recognized by providers per 100 elevated blood pressures measured) and the delayed diagnosis of actionable laboratory results rate (delayed actions on laboratory results per 100 abnormal laboratory results received). Since the individual-level outcome will be binary (missed/delayed diagnosis or not), we will apply mixed-effects logistic models for testing the three primary hypotheses during the first study year and for testing secondary hypotheses. The clinic-specific intercept will be considered random to take into account potential correlations of outcomes from the subjects within the clinics. We will test each of the three main effects using a mixed-effects including factors such as baseline diagnostic error rates, patient volume, number and training of physician or physician assistant-level providers, number of nursing and office staff, university-affiliation, EHR availability, presence of trainees, and prior work improving these diagnostic errors.

Power Analysis: Assuming a two sided alpha level of 0.05 and >80% power, we calculated the effect size we could detect for each of the 3 diagnostic error primary outcome measures, comparing the 10-20 intervention practices, given the stepped wedge design, to the 10-20 control practices using the above models, and the QIC methodology and preliminary data. 1) Missed diagnosis of depression: If each practice screens 17 adolescent charts a month, we are able to detect an effect size of 2.4% or a reduction in the diagnostic error rate as small as 33% (intra-class correlation coefficient (ICC)=0.005). 2) Missed diagnosis of pediatric elevated blood pressure: If each practice screens 10 patient charts with elevated blood pressure a month, we are able to detect an effect size of 12% or a reduction in the diagnostic error rate as small as 13% (ICC=0.1). 3) Delayed diagnosis of actionable laboratory results: If each practice collects 10 patient charts with abnormal laboratory values a month, we are able to detect an effect size of 12% or a reduction in the diagnostic error rate as small as 13% (ICC=0.1). Although we are testing three outcomes, we do not correct the alpha level for multiple testing since the study subjects will most likely be different across the three outcome comparisons.

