# Methods:

This proposal aims to identify systems solutions for reducing harmful pediatric diagnostic errors. We will perform a prospective, stepped wedge cluster randomized controlled trial to test the hypothesis that QIC strategies can reduce three specific diagnostic errors in a national group of ambulatory pediatric primary care practices. These data will inform future diagnostic errors. Baseline data from the QIC will identify incidence data for errors in 3 separate stages of the diagnostic process: symptoms (missed diagnosis of adolescent depression), signs (missed diagnosis of pediatric elevated blood pressure) and diagnostic tests (delayed diagnosis of actionable laboratory results). Each of these diagnostic errors represents missed opportunities to recognize abnormal diagnostic findings. Human subjects' protection will be completed at the CHAM to cover the researchers and data analysis and at the American Academy of Pediatrics to cover all practices, as completed for prior QuIIN projects.

The goal of this proposal is to reduce diagnostic errors by tracking diagnostic errors rates (outcomes measures) and reliably performing best practices for diagnosing adolescent depression, pediatric elevated blood pressure and actionable laboratory results (process measures). In order to reduce overall data collection burden on practices and to increase engagement of practices that would have been in the control group, we have changed the study design. These changes do not affect the statistical power of the study. The intervention will consist of implementing QIC methodology in all practices to assist teams in reliably performing the processes that will reduce the diagnostic error outcomes via evidence-based tools. Practices will be randomized into three groups, with each group intervening on 1 diagnostic error and serving as the control group for a second diagnostic error. After 8 months of participation, each group will begin intervening on the diagnostic error they were a control group for, continue intervening on their original diagnostic error, and function as the control group for the third diagnostic errors. In the final 8 months of the QIC, all three groups will intervene on all three diagnostic errors.

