All practices will participate in the QIC for the full 2 years of the study. They will attend an initial 2-day interactive webinar learning session where they will learn QI methodology. enhance and practice QI skills, identify local 30-60 day aims for the diagnostic error they are intervening on first, increase their understanding of diagnostic errors and these errors in particular, and create systems for standardized data collection and data entry. Practices will submit monthly data on their intervention and control diagnostic errors but only receive centralized data feedback, coaching or collaborative involvement regarding their intervention error. (Figure 1) We acknowledge that error measurement in the baseline and intervention periods may introduce an intervention effect, but we have no reason to believe this effect will be different for the intervention and control practices. As noted above, after 8 months, practices will participate in a second 2-day video conference learning session, continue to intervene on their first error, begin to intervene on the error they were a control group for and begin to collect control data for the third diagnostic error. Including the control group in the QIC ensures that harm is prevented in the maximum number of patients and that clinical equipoise is met, as we believe this intervention will reduce errors. This stepped wedge design with two steps allows for the primary outcome comparison (diagnostic errors in intervention versus control) and secondary outcome comparisons: 1) diagnostic error rates in second wave participants), 2) Sustainability after first eight months and 3) collaborative effect for second wave practices. These secondary outcome comparisons will shed light on the effectiveness and sustainability of QICs and inform future collaborative designs.

Given concerns about practice attrition, we will additionally recruit a second wave of practices to join the collaborative. The three phase quality improvement research model lends itself to simply on-boarding a new group of practices and integrating them into the project in Phase 2 which would begin in June of 2016. The up to 15 Wave 2 practices would be recruited

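### The primary model's first-year window crosses the month-8 switch, with no rule for coding later months and no calendar-time term listed

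*Combined protocol and SAP*

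**What the plan says.** Section 7, Statistical Models, defines exposure as follows: "The primary independent variable will be assignment to the control or QIC group". The window is the first study year ("we will apply mixed-effects logistic models for testing the three primary hypotheses during the first study year"). The clinic intercept is random. The adjustment list is open-ended, "including factors such as baseline diagnostic error rates, patient volume", and continues with staffing, affiliation, EHR, trainees and prior work. Every named item is a practice characteristic or a baseline rate. Section 8 adds only variables found to differ at baseline.

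Section 2, Methods, describes a design in 8-month phases: "After 8 months of participation, each group will begin intervening on the diagnostic error they were a control group for". At that point each group also starts giving control data for its third error. Then: "In the final 8 months of the QIC, all three groups will intervene on all three diagnostic errors". The text after Table 1 adds "All practices will participate in the QIC for the full 2 years of the study", so three 8-month phases fill the two years. The same text lists "Sustainability after first eight months" among the secondary comparisons.

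For any one error the layout is:

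| Group | Months 1-8 | Months 9-16 | Months 17-24 |
|---|---|---|---|
| A | intervene | intervene | intervene |
| C | control | intervene | intervene |
| B | no data | control | intervene |

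**The concern.** A 12-month window that starts with the QIC takes in 8 months of A against C, then 4 months in which A and C both intervene and B is the control. The plan does not say whether C's months 9-12 count as control or as QIC. It also does not commit to comparing practices within the same calendar period. In a stepped-wedge design, intervention time falls later on average than control time, so a drift common to all practices passes into the effect estimate unless the model includes time.

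The protocol itself gives a reason to expect drift. It accepts that "error measurement in the baseline and intervention periods may introduce an intervention effect" and relies on this being equal in both arms. If such an effect builds up over months, it cancels only when arms are compared within the same period.

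The primary result for all three hypotheses is at stake, because the same data can yield different estimates depending on a choice that the plan leaves unmade.

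**Working it through.** **Inputs.** From section 7, Power Analysis: 17 charts a month at ICC 0.005 (depression); 10 a month at ICC 0.1 (blood pressure, laboratory results); two-sided 0.05, 80% power; 10-20 v 10-20 practices; detectable effects 2.4, 12 and 12 points. From section 2: 30 practices in three equal groups gives 10 per group. Base rates: depression 2.4/0.33 = 7.3% (implied by the power text) or 10% x 25% = 2.5% diagnosed (section 1); blood pressure 74-87% and laboratory results up to 26% (section 1); 12/0.13 = 92% (implied by the power text).

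**The plan's own figures.** Detectable difference = 2.80 x sqrt[(v1+v2) x DE/(n x M)], where v = p(1-p), M is charts per practice and DE = 1+(M-1) x ICC.
- 20 v 20 with 8 months each: 2.35 (7.3 v 4.9%), 11.5 (87 v 75%), 11.7 (26 v 14.3%).
- 15 v 15 over 12 months: 2.43 (7.3 v 4.9%), 11.5 (92 v 80%).

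Both are close to 2.4 and 12, so the stated figures do not settle which window was meant.

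**Months 1-8 only (A v C, 10 v 10).**
- Blood pressure and laboratory results: M = 80, DE = 1+79 x 0.1 = 8.9. For 26 v 14.3%: 2.80 x sqrt(0.3149 x 8.9/800) = 16.6. For 92 v 80%: 14.3. For 74 v 52%: about 20.
- Depression: M = 136, DE = 1+135 x 0.005 = 1.675. For 7.3 v 4.9%: 2.80 x sqrt(0.1143 x 1.675/1360) = 3.32. For 2.5 v 4.9%: 2.62.
- With the 25 retained practices (8.33 per group, factor sqrt(10/8.33) = 1.10): 2.9-3.6 and 16-22.
- Adding Wave 2's own first 8 months, about 13 v 13 (factor sqrt(10/13) = 0.88): 2.3-2.9 and 12.5-17.

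**Current status, no time term.** Generalised least squares was applied to the layout above, with a random clinic intercept and a linear common trend. The table gives the bias per point of trend per 8 months.

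| Window | ICC 0.1 | ICC 0.005 | With month or phase terms |
|---|---|---|---|
| 12 months | 0.594 | 0.239 | 0 |
| 9 months | 0.300 | 0.084 | 0 |

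The 12-month values can be bracketed by hand.
- Ignoring clustering, intervention months average (120 x 6.5 + 40 x 10.5)/160 = 7.5 and control months (80 x 4.5 + 40 x 10.5)/120 = 6.5. The gap is 1 month, or 1/8 = 0.125.
- Using only within-practice change, C's before-after gap is 10.5 - 4.5 = 6 months, or 6/8 = 0.75.

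Both 0.239 and 0.594 lie between these limits. The 9-month row assumes that about 3 baseline months count in the study year, as in Wave 2's March enrolment and June start.

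**False positives.** Simulation with no true effect, 1,000 data sets per cell, logistic random-intercept model, 12 months, no time term:
- laboratory results: 5%, 7% and 11% at trends of 1, 2 and 3 points;
- depression at a 2.5% rate: 7%, 8% and 16% at 0.5, 1 and 2 points.

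With a phase term the rates are 4-7%. Over 9 months without one they are also 4-7%. The simulation error at a true 5% is sqrt(0.05 x 0.95/1000) = 0.7 points, so only the larger trends stand clearly above the background.

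**Initial assignment kept, A v C.** An immediate constant effect is recovered to 8/12 = 67% over 12 months, or 8/9 = 89% over 9. Hypothesis 1 (40% of 7.3% = 2.9 points) becomes 1.9 or 2.6.

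**Current status plus a phase term, 12 months, 30 practices.** The bias from a common trend is zero. Detectable effects are 2.38 points for depression (7.3 v 4.9%) and 6.4 (92 v 80%) to 8.8 (74 v 52%) for blood pressure and laboratory results.

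**The case against.** The window is named, so it cannot be called undefined. The fault is that it crosses the switch. The first-year wording may be carried over from before the design change that section 2 describes (an inference).

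The covariate list is open, so the analyst may add a period term. A reader might infer that no reading of the plan gives both an unbiased estimate and the stated precision. The documents do not support that: current-status coding with a phase term, inside the first year, is free of common-trend bias and meets 2.4 and 12 with 30 practices. The list permits such a term but does not commit to it.

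A reader might also infer that switched practices will be analysed as controls and the effect diluted. That reading is strained. Switched practices receive the intervention, and the 10-20 practices per side, which the power text ties to the stepped wedge, fit current status: across phases 1-2, 20 practices intervene at some time and 20 serve as control at some time. The blood pressure hypothesis would survive dilution in any case: 22-26 points becomes 15-17, still above 12.

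Finally, the harm depends on a trend that the documents do not give, and over 9 months no inflation was seen. This objection stands and limits the size of the point. It does not remove the need to fix the primary model in advance.

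**Conclusion.** The point holds as a specification gap in the primary model that has a real but conditional bias risk. The first-year window, counted from the start of the QIC, runs 4 months past the switch. No rule covers those months, and no time term is listed. On the natural current-status reading, 0.59 (ICC 0.1) or 0.24 (ICC 0.005) of each point of common trend per 8 months is taken as QIC effect. A favourable trend inflates the effect and an adverse one hides it. The distortion matters mainly with a 12-month window and a trend of about 2 points or more. It does not follow that the trial's result will be biased. Retreating to months 1-8 is clean but does not reach the stated detectable effects at 10 v 10.

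These figures assume 10 practices per group, a linear trend, an immediate constant effect, and a risk-difference approximation to the logistic model.

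**What to change.** In section 7, Statistical Models:
- Define exposure for each error as a practice-by-month indicator of intervening on that error.
- Add fixed effects for calendar period (month or phase) and for wave, and keep the random clinic intercept.
- Replace the first-year window with the phases that have concurrent controls: phases 1-2 for Wave 1, stating how Wave 2 control data are used. The period term must come with this change, because without it the bias over phases 1-2 rises to 0.86 per point at ICC 0.1.
- Report months 1-8 as a sensitivity analysis, since it needs neither a time term nor a constant effect.
- Recompute the Power Analysis for this model. If months 1-8 is meant to be primary, say so and restate the power at 10 v 10.

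**Cost.** No new data. Over 12 months the standard error rises from 2.37 to 2.94 points (24%) for laboratory results at 26%, and from 0.53 to 0.55 (4%) for depression at 2.5%, against the same model without period terms. The model also assumes one constant effect from the first month of intervening.

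Over phases 1-2 with 30 practices, the detectable effects are 1.7-2.1 points for depression (about 1.4 if the variance at 2.5% is used for both arms) and 5.6-7.7 for blood pressure and laboratory results. If practice effects correlate 0.8 between phases (an assumption) and 25 practices remain, they are 1.8-2.3 and 8.5-11.7. All lie within 2.4 and 12.

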The proposal will focus on 3 specific, high-risk, pediatric ambulatory diagnostic errors each representing a unique dimension of diagnostic assessment: evaluation of symptoms, evaluation of signs and follow-up of diagnostic tests. Adolescent depression (i.e. symptoms) affects nearly 10% of teenagers, is misdiagnosed in almost 75% of adolescents and causes significant morbidity. Pediatric elevated blood pressure (signs) is misdiagnosed in 74-87% of patients, often due to inaccurate application of blood pressure parameters that change based on age, gender and height. Actionable pediatric laboratory values (diagnostic tests) are potentially delayed up to 26% of the time in preliminary investigations and 7-65% in adults, leading to harm and malpractice claims.

We propose to conduct a multisite, prospective, stepped wedge cluster randomized trial testing a quality improvement collaborative (QIC) intervention within the American Academy of Pediatrics' Quality Improvement Innovation Networks (QuIIN) to reduce the incidence of pediatric primary care diagnostic errors. QuIIN is a national network of over 300 primary care practices, ranging from tertiary care academic medical centers to single practitioner private practices, interested in and experienced with QICs. Because many processes are likely to be common across diagnostic errors in outpatient settings, a multifaceted intervention, such as a QIC, has a high likelihood of success and broad applicability across populations. Preparatory inquiries to QuIIN primary care providers suggest high interest in reducing these 3 diagnostic errors and provider agreement with randomization to evaluate diagnostic error interventions.

The purpose of this IRB application is to cover the data analysis of the QIC data generated in this project. The AAP's IRB will cover each individual pediatric clinic, the data collection and the conduct of the study.

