#### 2. Study Design: Objectives:

# Primary

- To determine whether a QIC consisting of evidence-based best-practice methodologies, mini-root cause analyses, data sharing, and behavior change techniques, is associated with a reduction in 3 specific diagnostic error rates in a national group of pediatric primary care practices.
  - Hypothesis 1: Implementation of a QIC will lead to a 40% reduction in missed diagnosis of adolescent depression.
  - Hypothesis 2: Implementation of a QIC will lead to a 30% reduction in missed diagnosis of pediatric elevated blood pressure.
  - Hypothesis 3: Implementation of a QIC will lead to a 45% reduction in delayed diagnosis of actionable laboratory results.

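### The laboratory detectable effect (12%, or a 13% reduction) needs a baseline near 92%, but the plan reports no laboratory delay rate above 65%

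*Combined protocol and SAP*

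**What the plan says.** The Power Analysis paragraph (Combined protocol and SAP, section 7) uses a two-sided alpha of 0.05 and more than 80% power, "comparing the 10-20 intervention practices, given the stepped wedge design, to the 10-20 control practices". It says the figures were obtained "using the above models, and the QIC methodology and preliminary data". For each primary outcome it gives two numbers joined by the word or:

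- Depression, 17 charts a month, ICC 0.005: "able to detect an effect size of 2.4% or a reduction in the diagnostic error rate as small as 33" percent.
- Blood pressure, 10 charts a month, ICC 0.1: 12%, or 13%.
- Laboratory results, 10 charts a month, ICC 0.1: "values a month, we are able to detect an effect size of 12% or a reduction in the diagnostic error rate as small as 13" percent.

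The paragraph does not state the baseline rates, the number of practices within 10-20, or the months of data counted.

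Rates appear in section 1 (Background/Significance). Elevated blood pressure "is misdiagnosed in 74-87% of patients". Actionable laboratory values "are potentially delayed up to 26% of the time in preliminary investigations and 7-65% in adults". Hypothesis 3 (section 2, Primary objectives) reads: "Implementation of a QIC will lead to a 45% reduction in delayed diagnosis of actionable laboratory results".

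**The concern.** An absolute difference and a relative reduction that describe the same effect fix the baseline: it is the first divided by the second. Two outcomes with very different error rates cannot share both an absolute and a relative figure. Yet the laboratory line repeats the blood-pressure line exactly (12%, 13%, ICC 0.1), although section 1 puts blood-pressure misses at 74-87% and paediatric laboratory delays at no more than 26%.

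This is the only sensitivity that the plan states for one of its three primary outcomes. A reader who takes it at face value will believe the trial can detect a fall of about one eighth in laboratory delays, and may later read a null result as excluding a modest benefit. Because the baseline, practice number and months are not given, the reader cannot correct the figure.

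**Working it through.** **1. Implied baselines (absolute / relative, with rounding limits).**
- Depression: 0.024/0.33 = 7.3% (0.0235/0.335 = 7.0% to 0.0245/0.325 = 7.5%).
- Laboratory: 0.12/0.13 = 92.3% (0.115/0.135 = 85.2% to 0.125/0.125 = 100%).

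The lowest laboratory value, 85%, is 20 points above the highest laboratory rate in section 1 (65%).

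**2. Method for checking the figures.** The inputs are alpha 0.05 two-sided, 80% power, the stated ICCs and charts per month, and k practices per arm from the stated 10-20. I assume 8 months of data, the length of one phase in section 2 (Methods), so m = 80 charts per practice (136 for depression). Effective n per arm = k·m / [1 + (m − 1)·ICC]. Power = Φ[(d − 1.96·SE0)/SE1], where d = p1 − p2, SE0 = √[2·p̄(1 − p̄)/n] and SE1 = √{[p1(1 − p1) + p2(1 − p2)]/n}. The detectable difference is the d that gives 0.80.

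**3. Reproducing the plan's other two pairs (k = 20).**
- Depression: n = 20·136/(1 + 135·0.005) = 1,624. From 7.3% the detectable difference is about 2.35 points, or 32%. Stated: 2.4%, 33%.
- Blood pressure: n = 20·80/(1 + 79·0.1) = 179.8. From 87% it is 11.5 points, or 13.2%. Stated: 12%, 13%.

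So the absolute/relative reading fits, and these inputs are close to whatever the plan used.

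**4. The laboratory line with the same inputs (n = 179.8).**
- From 26%: d = 0.118, p2 = 0.142, SE0 = 0.0423, SE1 = 0.0418; (0.118 − 0.0828)/0.0418 = 0.84, so power is 0.80. The detectable difference is **11.8 points, and 11.8/26 = 45%**. Hypothesis 3's reduction is 0.45 × 26 = 11.7 points.
- From 65%: 14.5 points, or 22%.
- A 13% reduction from 26% is 0.13 × 26 = 3.4 points: (0.0338 − 0.0887)/0.0452 = −1.21, so power is **about 11%**.
- With 10 v 10 practices (n = 89.9), from 26%: 16.0 points, or 61%.

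By plain division, 12 points is 46% of 26% and 18.5% of 65%, and it exceeds a 7% rate altogether.

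**5. Stepped-wedge approximation.** Linear mixed model, baseline 26%, ICC 0.1, first year taken as 12 months (80 charts, then 40). There are 25 retained Wave 1 practices in three groups, plus 15 Wave 2 practices joining at month 8.

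| Model | Detectable reduction |
|---|---|
| Clinic intercept only | about 26% (25.8% of 26% = 6.7 points) |
| Period effects added, cluster autocorrelation 1.0 | 31% (8.0 points) |
| Period effects added, cluster autocorrelation 0.5 | 41% (10.7 points) |

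The answer depends on the model, but none of these gives 12 points together with 13%.

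**The case against.** Four points can be made for the plan.

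First, effect size is not defined, and the unpublished preliminary data might hold a higher laboratory rate. The absolute/relative reading nevertheless reproduces the other two pairs, and section 1 itself reports the preliminary laboratory investigations as up to 26%.

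Second, a reader might infer that a 13% reduction is out of reach under any layout or at any documented rate. The documents do not support that. The Statistical Models paragraph names a random clinic intercept and lists no period term. With a clinic intercept only, the first-year detectable reduction from 65% is about 12.0%. Over 24 months, 30 + 15 practices have about 81% power for a 13% reduction from 26%. Neither result repairs the pair: 13% of 26% is 3.4 points and 13% of 65% is 8.5 points, not 12.

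Third, a reader might infer that the blood-pressure line is wrong too. It is not shown to be: its pair reproduces at 87%, inside the documented 74-87%.

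Fourth, Hypothesis 3 targets 45%, not 13%, and 12 points is reproducible at 26%, so the design need not be inadequate. That stands. But the 20 v 20 comparison is a simplification, since in the first phase one third of practices intervene on a given error and one third serve as its controls. The agreement at 12 points also needs the top of the 10-20 range.

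**Conclusion.** The laboratory pair is internally inconsistent: no laboratory rate reported in the plan makes 12% and 13% describe the same effect. That conclusion needs only division and section 1.

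Which figure is wrong is a matter of likelihood. The 11.8 points (45%) found at a 26% baseline points to the 13% as the error, possibly copied from the blood-pressure sentence. That rests on assumptions: 26% (an upper figure in section 1) as the baseline, 8 months of data, 20 practices per arm and a parallel design-effect formula. If the 13% is the error, the stated relative sensitivity is too optimistic by a factor of about three and a half in that check (45/13 = 3.5), and by two to three in the first-year stepped-wedge approximation (26/13 = 2.0 to 41/13 = 3.2).

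This is a misstated sensitivity and not evidence of a failed design. A reader might also take it as disproving the Methods statement "These changes do not affect the statistical power of the study". It does not: that sentence compares the designs before and after the change, and says nothing about whether 12% and 13% agree.

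**What to change.** In the Power Analysis paragraph of section 7:

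1. State the laboratory baseline rate and its source, the number of practices within 10-20, and the months of data assumed.
2. Recompute the absolute and the relative laboratory detectable effects from that one baseline, under the planned mixed model, the stepped-wedge layout and the practices actually retained. Say whether the model includes period effects, because the result depends on them.
3. Replace the 12%/13% pair with the result. For orientation, at 26% the parallel check gives about 12 points, or 45%.

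The cost is confined to the text. At a 26% baseline in the first year, the stated relative sensitivity becomes less favourable than 13%. No practices, charts or visits are added.
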